12 STATISTICAL METHODS

This section outlines the statistical analysis strategy and procedures for the study. Specific details of the primary and key secondary analyses will be provided in the Statistical Analysis Plan (SAP). If, after the study has begun, but prior to the final analysis, important changes are made to the protocol that affect principal features of the primary or key secondary analyses, then the protocol and/or SAP will be amended, as appropriate. Any other changes made to the planned analyses after the protocol and SAP have been finalized, along with an explanation as to when and why they occurred, will be listed in the Clinical Study Report (CSR) for the study. Post hoc exploratory analyses will be clearly identified in the CSR.

12.1 Populations

12.1.1 Efficacy Analysis

The FAS population will serve as the primary population for the analysis of tumor response and other efficacy-related data. Subjects will be excluded for FAS for the following reasons:

- No baseline data
- Failure to receive at least one dose of tipifarnib
- No post-baseline endpoint data subsequent to at least 1 dose of study drug

12.1.2 Safety Analysis

The All Subjects as Treated (ASaT) population will be used for the analysis of safety data. The ASaT population consists of all enrolled subjects who receive at least one dose of tipifarnib. At least one laboratory or vital sign measurement obtained subsequent to at least one dose of study drug is required for inclusion in the analysis of a specific safety parameter. To assess change from baseline, a baseline measurement is also required.

12.2 Endpoints

12.2.1 Efficacy

[figure not shown]
The objective response rate will be estimated for each tumor histology type evaluated. The estimate of the objective response rate will be calculated based on the maximum likelihood estimator (i.e., crude proportion of subjects whose best overall response is CR or PR). The estimate of the objective response rate will be accompanied by 2-sided 95% exact binomial confidence intervals.

The duration of objective response will be calculated for subjects who achieve CR or PR. For such subjects, the duration of objective response is defined as the number of days from the start date of PR or CR (whichever response is achieved first) to the first date that progressive disease is objectively documented. Disease progression will be determined by the Investigator using the Lugano Classification and/or mSWAT. The duration of objective response will be right-censored for subjects who achieve CR or PR and meet 1 of the following conditions: 1) non-protocol anticancer treatment started before documentation of disease progression, 2) death or documented disease progression after more than 1 missed disease assessment visit, or 3) alive and does not have documentation of disease progression before a data analysis cutoff date.

The duration of objective response will be summarized descriptively using the Kaplan-Meier method. The 50th percentile of the Kaplan-Meier distribution will be used to estimate the median response duration.

Progression free survival will be defined as the time (in months) from enrollment to either first observation of progressive disease or occurrence of death due to any cause within 126 days (approximately 2 time intervals for tumor assessments) of either first administration of tipifarnib or the last tumor assessment. In subjects without a progression date or with a death date more than 126 days after the first administration of study drugs or the last tumor assessment, the PFS time should be censored on the date of last tumor assessment or date of first administration of study tipifarnib. Progression free survival analyses should consider tumor assessments after treatment discontinuation or metastatic surgery.

The PFS will be summarized descriptively using the Kaplan-Meier method. The 50th percentile of the Kaplan-Meier distribution will be used to estimate the median PFS.

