11.7.1 Follow Up after Disease Progression

Upon disease progression, all subjects will be followed approximately every 12 weeks for survival and the use of subsequent therapy until either death or 12 months after accrual of the last study subject, whichever occurs first. Information on survival and subsequent anticancer therapy may be collected by phone.

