8.2. Secondary Efficacy Analysis

The secondary efficacy analysis will focus on DOR and PFS analysis in the study population (FAS analysis data set), as well as on subgroup analysis of ORR, PFS, and DOR in genetic sub-types (AITL, PTCL-NOS, CXCL12+, and Other).

The duration of the response will be calculated for subjects who achieve an objective response (either CR or PR, whichever comes first). For such subjects, the duration of the objective response is defined as the number of days from the start date of the objective response to the first date of either documented progressive disease or death. All efforts will be made to objectively define the endpoint by collecting the necessary data and reducing the likelihood of missing data. In the event of a maintained response, the DOR will be censored at the last evaluable non-PD assessment.

Disease progression will be determined by the investigator using the primary efficacy endpoint assessment. Progression free survival will be defined as the time (in months) from first dose (Cycle 1 Day 1) to the minimum date of progression or death, if death occurred within 126 days

³ Wilson, E. B. (1927). "Probable inference, the law of succession, and statistical inference". *Journal of the American Statistical Association*. 22 (158): 209–212.

⁴ Clopper, C.; Pearson, E. S. (1934). "The use of confidence or fiducial limits illustrated in the case of the binomial". *Biometrika*. 26 (4): 404–413.

of the last treatment or assessment. If the subject goes off study with no documentation of PD, the censoring date will be the date of the last evaluable assessment.

Sensitivity analyses may be conducted to explore the effect of different censoring on DOR and PFS.

The duration of the objective response and progression free survival will be analyzed using the Kaplan-Meier (KM) method. 95% CI for KM curve will be constructed using Greenwood's⁵ formula in the log-log scale.

The median DOR and PFS will be evaluated using the 50th percentile of KM distribution. 95% CIs for the median will be constructed based on a robust nonparametric method of Brookmeyer and Crowley⁶.

Summary tables and advanced data visualizations will be used for presenting KM plots, 95% CIs for probabilities of surviving X months, and a median survival estimate with its 95% CIs. The analysis will be conducted on FAS (primary) [REDACTED] populations.

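### Protocol 12.2.1 makes some PFS outcomes both events and censored times; SAP 8.2 removes most of the conflict but leaves an overlap and undeclared changes

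*Protocol*

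**What the plan says.** Protocol 12.2.1 first defines the event. The clock start and the progression component read: "Progression free survival will be defined as the time (in months) from enrollment to either first observation of progressive disease". Death is the second component, and it counts only inside a window: "occurrence of death due to any cause within 126 days (approximately 2 time intervals for tumor assessments) of either first administration of tipifarnib", with the date of the latest tumor assessment as the alternative reference point. The following sentence defines censoring. It opens "In subjects without a progression date or with a death date more than 126 days after the first administration of study drugs", adds the last tumor assessment as an alternative reference date, and concludes that "the PFS time should be censored on the date of last tumor assessment or date of first administration of study tipifarnib". No order of precedence is given.

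SAP 8.2 words the endpoint differently. The clock starts at first dose, and PFS runs "to the minimum date of progression or death, if death occurred within 126 days"; here the window is counted from the latest treatment or assessment. The SAP's censoring rule is: "If the subject goes off study with no documentation of PD, the censoring date will be the date of the last evaluable assessment".

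The SAP's section on changes from the protocol (SAP 14) mentions no change to PFS.

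**The concern.** An event rule and a censoring rule should be mutually exclusive. In Protocol 12.2.1 they overlap in two places. The late-death condition does not exclude subjects who have already progressed, and the no-progression condition does not exclude subjects whose death has just been counted as an event.

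Both kinds of record will occur. Deaths after progression are collected, because "Upon disease progression, all subjects will be followed approximately every 12 weeks for survival" (Protocol 11.7.1), and deaths before progression are expected in relapsed or refractory PTCL. In both overlaps, following the censoring sentence turns a failure into a censored time, which pushes the Kaplan-Meier median upward.

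PFS belongs to the first secondary objective. SAP 7.3 also compares it with PFS on the last prior therapy, and a PFS contrast was part of the stated reason for adding the CXCL12+ cohort (Protocol 8.1 and 12.4).

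**Working it through.** No stated figure is to be reproduced; the question is one of logic, so test records are run through the two protocol sentences.

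**Rules as written.** Let D be the day of death and L the day of the last tumor assessment, both counted from first dose.
- Event: progression (PD), or death with D ≤ 126 or D − L ≤ 126.
- Censored: no PD, or a death with D > 126 or D − L > 126. The text does not say whether one late interval is enough (either-date reading) or both are needed (both-dates reading), so both were tried.

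| Record | Event sentence | Censoring sentence |
|---|---|---|
| PD day 50, dies day 250 | event | censored on both readings (250 > 126; 250 − 50 = 200 > 126) |
| PD day 50, dies day 150 | event | censored on the either-date reading only (150 > 126; 150 − 50 = 100) |
| PD day 50, dies day 100 | event | not censored |
| PD day 50, alive | event | not censored |
| No PD, no scan, dies day 60 | event | censored |
| No PD, scan day 50, dies day 100 | event | censored |
| No PD, scan day 160, dies day 200 | event (200 − 160 = 40) | censored |
| No PD, scan day 160, dies day 400 | not an event (400 − 160 = 240) | censored |
| No PD, scan day 160, alive | not an event | censored |

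Five of the nine records are classified both ways on at least one reading. Progression followed by a death on or before day 126 is not affected.

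**The same records under SAP 8.2.** The late-death clause is gone, so all four PD records are events only. The three deaths inside the window without PD are events by the definition. Each of those subjects could still be said to leave the study without documented PD, and the censoring sentence carries no exception for them. SAP 6.4 treats dropouts without an event as censored, which points to counting these deaths as events only.

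**Subjects with no post-dose scan.** The secondary PFS analysis uses the FAS, which requires a post-dose response assessment (SAP 5), so they are not in it. They are in the ASaT population used for the prior-therapy comparison in SAP 7.3. For a living subject of this kind, the last evaluable assessment is either the screening scan, up to 28 days before first dose, giving a PFS time as low as −28 days, or it does not exist. The protocol's option of censoring at first dose would have covered this. Protocol 5.2 reports 12 of 15 and 11 of 16 expansion-cohort subjects evaluable, so (15 − 12) + (16 − 11) = 8 of 31 were not evaluable at that time; some may have been scanned later.

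**Window anchor.** Take a subject with no PD, last scan on day 160, last dose on day 180 and death on day 300. Protocol: 300 > 126 and 300 − 160 = 140 > 126, so not an event. SAP: 300 − 180 = 120 ≤ 126, so an event.

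**Illustrative size of the protocol sentence.** Scan days follow from Day 22 of Cycles 2, 4, 6 and 9, as 28 × (cycle − 1) + 22 = 50, 106, 162 and 246, then every 84 days. Median time to progression was set at 50 or 134 days, the two median PFS values in Protocol 5.2. The following are assumptions: exponential times, median survival after PD of 90 to 540 days, cutoff uniform over 365 to 1,100 days, and a pre-progression death hazard one quarter of the progression hazard. Qualifying deaths without PD were kept as events, so only the late-death clause is at work.

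| | Either-date reading | Both-dates reading |
|---|---|---|
| PD subjects censored | 45% to 79% | 33% to 50% |
| Median PFS, 50-day scenario (intended rule: 50 days) | 106 to 111 days | 92 to 106 days |
| Median PFS, 134-day scenario (intended rule: 114 to 117 days) | 228 to 371 days | 162 to 223 days |

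A second set of assumptions (median survival after PD 180, 365 or 599 days; follow-up 365 to 1,095 days; mean time to death without PD 1,500 days) gave 41% to 75% of PD events censored when the 126 days are counted from first dose, and 31% to 50% when counted from the last assessment.

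**The case against.** The strongest reply is that the SAP governs the analysis. Protocol 12 leaves the specific details of the key secondary analyses to the SAP, and SAP 1 describes itself as the fuller technical account. A reader might infer from the simulated shifts that the planned PFS medians are badly inflated. The documents do not support that: SAP 8.2 has no late-death clause, so those figures describe the protocol sentence only. SAP 6.4 supports treating a qualifying death as an event, and FAS membership removes the no-scan subjects from the secondary analysis. These replies stand. They do not make the protocol text consistent, and they do not supply the exception missing from the SAP's own censoring sentence.

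The clock-start difference may also be nominal. The protocol glosses enrolled as having received tipifarnib in the synopsis, 8.1 and 12.4. Its safety population in 12.1.2 separates the two, however, so a clarification is fair but a clear contradiction is not shown.

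A sensible analyst would probably infer the intended rule. That is likely, but the obvious repair of changing the censoring sentence's or to and would fail: a living subject without PD has no death date and would then be neither an event nor censored.

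Finally, the simulated medians are fragile. An exponential median of 50 days falls exactly on the first scan day, so modest censoring is enough to move the estimate on. Survival after progression, the rate of death before progression and the follow-up time are not in the documents.

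**Conclusion.** Protocol 12.2.1 is wrong as written. It classifies documented PD followed by a late death, and a qualifying death without PD, as both event and censored.

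For the analysis planned in the SAP, the first conflict is gone and the second is probably resolved. What remains is the unqualified censoring sentence in SAP 8.2, the lost first-dose fallback (relevant only to the ASaT comparison in SAP 7.3), and a new clock start and window anchor that SAP 14 does not declare.

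The expected effect under the SAP is small. If its censoring sentence were nevertheless applied to qualifying deaths, the exposure would equal the share of deaths without PD, which the documents do not give. It was 6% to 15% of PFS events with an assumed mean time to such death of 1,500 days, and 23% to 28% of subjects under the much heavier hazard assumed above. PFS is secondary and descriptive; the ORR test does not depend on any of this.

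**What to change.** State one mutually exclusive rule in both documents:
- Documented PD is an event, whatever the date of any later death.
- Death without PD inside the window is an event.
- Subjects with no documented PD who are alive, or who die outside the window, are censored at the last evaluable post-dose tumor assessment, or at first dose if there is none.

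Applied to the nine records, this gives seven events only (four PD, three qualifying deaths) and two censored only.

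Start the clock at first dose in both documents, name one anchor for the 126-day window, and list the PFS changes in SAP 14. The cost is SAP wording and a short protocol clarification, with no new data. Median PFS may come out shorter than under a literal reading of the protocol's censoring sentence.

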12.2.2 Safety and Tolerability

Safety and tolerability of tipifarnib will be assessed based on the following:

[figure not shown]
- Incidence, duration, and severity of treatment-emergent adverse events, serious adverse events, adverse events resulting in permanent discontinuation of study drug, and deaths within approximately 30 days from the last dose of study drug (or immediately before the administration of another anti-cancer treatment)
- Changes in vital signs including blood pressure, pulse, and temperature
- Changes in electrocardiogram results

Adverse events will be coded using the latest available version of the Medical Dictionary for Regulatory Activities (MedDRA). Treatment-emergent adverse events are defined as adverse events that start on or after the first dose of study drug and within approximately 30 days of the last administration of study drug. Adverse events will be summarized by the number and percentage of subjects who experienced the event, according to system organ class and preferred term. A subject reporting multiple cases of the same adverse event will be counted once within each system organ class and similarly counted once within each preferred term.

Unless specified otherwise, the denominator for these calculations will be based on the number of subjects who received at least one administration of tipifarnib, irrespective of the total number of doses or treatment cycles administered. These conventions will be appropriately modified to calculate AE incidence rates separately for each cycle that study therapy is administered. AE incidence rates may also be calculated based on other measures of subject exposure (e.g., total number of treatment cycles administered). AEs will also be summarized by NCI-CTCAE version 4.03 severity grade and by relationship to each study drug. Additional summaries may also be provided for SAEs, and events resulting in the permanent discontinuation of therapy. All AEs will be included in individual subject listings.

The incidence of grade 3 and 4 hematological toxicities (including neutropenia, thrombocytopenia, and anemia) will be provided by treatment cycle and across all treatment cycles. The toxicity grades for laboratory tests will be based on NCI-CTCAE version 4.03 criteria. The use of blood transfusions (platelets, red blood cells) and/or growth factor support will be reported. Similar analyses will be done for selected chemistry tests (including liver and renal function tests).

Vital sign results (blood pressure, pulse, and temperature) will be summarized descriptively for each scheduled and unscheduled protocol time point. Changes will be calculated relative to the assessments at baseline and on the first day of each cycle of therapy.

12.4 Sample Size Determination

A two-stage study design was used in the initial cohort of PTCL subjects without histological or genetic selection in order to minimize the number of study subjects treated if tipifarnib were to be not efficacious. This design is intended to allow the termination of accrual in case of unacceptably low efficacy after the first subjects are evaluated in a Full Analysis Set (FAS) basis.

A two-stage design will be employed. Eleven initial study subjects will be enrolled; if 2-4 responses are observed, 7 additional subjects will be enrolled. At the completion of this cohort, treatment will be considered of further interest if the true ORR is higher than 10%. To determine the total trial size of the initial cohort of subjects, a response of interest of 30% is assumed. This design provides 80% power to detect a difference between 10% and 30% ORR at one-sided significance level of 0.087. Using this design, the probability of terminating the study at the end of stage 1 if the true ORR is 10% is 0.697 while the probability of terminating the study at the end of stage 1 if the true ORR is 30% is 0.113.

An AITL cohort will be enrolled ($N = 12$) according to Amendment 4 to the protocol. With this sample size, if 4 or more responses are observed, the probability that the true response rate in AITL subjects is at least 30% is 82.6% ([Table 6](#)).

Based on the observed antitumor activity during stage 1 and stage 2 of the study in which subjects who were found to have high levels of CXCL12 gene expression and reference CXCL12 3'UTR by retrospective analysis had better outcomes in terms of response and PFS compared to subjects with low CXCL12 expression and CXCL12 3'UTR variant sequences, a CXCL12+ cohort will be enrolled ($N = 12$) according to Amendment 6 to the protocol. With this sample size, if 2 or more responses are observed, the probability that the true response rate in CXCL12+ subjects is 10% or higher is at least 87% ([Table 7](#)).

It is assumed that the presence of CXCL12 3'UTR gene variants is of germinal, not somatic, origin. By default, CXCL12+ subjects are defined as those who present with reference CXCL12 reference gene sequence in a buccal swab assay and in whom no CXCL12 3'UTR variant or

unknown status is observed in subsequent tumor CXCL12 gene sequencing. Subjects who were enrolled in the CXCL12+ cohort based on CXCL12+ status in the buccal swab test and later demonstrated to have a somatic tumor 3'UTR CXCL12 sequence variant will be allowed to continue treatment but may be replaced and not included in the evaluable study population for efficacy analyses.

Upon the observation of 5 confirmed responses in the AITL cohort, and 5 confirmed responses in the CXCL12+ cohort, including 2 of them in subjects with tumors of AITL histology, the trial was amended to include up to 20 additional subjects with AITL and related T follicular helper cell tumors in the AITL cohort in order to further characterize the safety and tolerability of tipifarnib in this patient population. The choice of 20 additional subjects was empirical based on the relative rarity of the patient population and no statistical hypotheses will be tested in this extension. Including Amendment 7, up to 70 evaluable subjects in total may be enrolled (dosed).

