A preliminary assessment of the first 50 subjects enrolled into the current trial was recently published (Witzig 2019). In the initial stages of the study, a retrospective assessment had suggested a high-degree of anti-tumor activity of tipifarnib in AITL and in PTCL-NOS subjects whose tumors expressed high levels of CXCL12 and carried reference CXCL12 3'UTR sequences of the CXCL12 gene (Witzig 2017). The median progression-free survival (mPFS) in subjects with reference 3'UTR sequences (n = 8) was 134 days, vs. a median PFS of 50 days (n = 7) in subjects whose tumors expressed the rs2839695 A>G variant of the gene, which resulted in low levels of CXCL12 expression. Based on those findings, a cohort of PTCL NOS subjects with reference CXCL12 3'UTR and a cohort enrolling AITL subjects were added to the trial. These cohorts investigated prospectively whether selection for subjects with high CXCL12 expressing tumors enriches for the activity of tipifarnib. Of 15 subjects enrolled into the PTCL expansion cohort, 12 were evaluable for efficacy at the time of the report. In the per protocol set (PPS, or all subjects who received at least 1 dose of tipifarnib and had 1 post-baseline efficacy assessment) the objective response rate (ORR) was 41.7% (3 CR, 2 PR) and the clinical benefit rate (CBR) was 91.7% (3 CR, 2 PR and 6 SD). Four subjects of AITL histology were enrolled in the cohort. Of the 3 CRs observed, 2 were experienced by AITL subjects.

In the AITL expansion cohort, 16 patients were enrolled with 11 being evaluable for efficacy. The ORR in the PPS was 45.4% and the CBR was 72.7% (3 CR, 2 PR, 3 SD). If all AITL subjects enrolled in the study are considered (expansion cohort subjects plus the AITL subjects in the early phases of the trial, n = 23, 17 evaluable), the ORR was 52.9% and the CBR was 70.6% (5CR, 4PR, 3 SD).

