8 TRIAL DESIGN

8.1 Study Design

This Phase II study will investigate the antitumor activity in terms of ORR of tipifarnib in subjects with relapsed or refractory PTCL. Only consented subjects who meet all the eligibility criteria will be enrolled in the study. All screening evaluations will be completed within 4 weeks (28 days) of Cycle 1 Day 1. Any screening evaluation, including disease status, will need to be repeated if performed more than 4 weeks from Cycle 1 Day 1.

Up to 70 subjects may be enrolled (receive tipifarnib) in the study. The first 18 subjects may be of the following PTCL sub-types: PTCL, not otherwise specified (PTCL-NOS), angioimmunoblastic T-cell lymphoma (AITL), ALK-positive and -negative anaplastic large cell lymphoma (ALCL), hepatosplenic T-cell lymphoma, enteropathy-associate T-cell lymphoma

(EATL), extranodal natural killer (NK) T-cell lymphoma, nasal type and subcutaneous panniculitis-like T-cell lymphoma. The AITL expansion cohort (N=12) will enroll only subjects with AITL.

A two-stage study design for the first 18 subjects will be used in order to minimize the number of study subjects treated if tipifarnib were considered not sufficiently efficacious to grant further development in this subject population. This design is intended to allow the termination of accrual in case of unacceptably low efficacy after objective responses in the first 11 evaluable subjects (stage 1) assessed in a Full Analysis Set (FAS) basis. If 0-1 objective responses are observed after the first 11 evaluable subjects, the study will be closed to further enrollment. If 2-4 responses are observed, 7 additional subjects will be enrolled (stage 2). Treatment will be considered of further interest if at least 4 responses are observed (out of 18 subjects).

Based on the observed antitumor activity during stage 1 and stage 2 of the study (2 subjects enrolled with AITL and both subjects achieved a partial response), an AITL cohort will be enrolled (N = 12) according to Amendment 4 to the protocol. With this sample size, if 4 or more responses are observed, the probability that the true response rate in AITL subjects is at least 30% is 82.6%.

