Based on the observed antitumor activity during stage 1 and stage 2 of the study in which subjects who were found to have high levels of CXCL12 gene expression by retrospective analysis had a longer PFS compared to subjects with low expression, a CXCL12+ cohort will be enrolled (N = 12) according to Amendment 6 to the protocol. With this sample size, if 2 or more responses are observed, the probability that the true response rate in CXCL12+ subjects is at least 10% is at least 89%.

Based on the high antitumor activity observed in AITL subjects in the AITL cohort and other portions of the study, enrolment in the AITL cohort has been expanded to include up to 20 additional subjects with tumors of AITL and related T follicular helper cell histologies in order to further characterize the safety and tolerability of tipifarnib in this relatively rare population. The selection of 20 subjects was empirical and no statistical hypotheses will be tested. Descriptive statistics will be used to report response rate.

Eligible subjects will receive tipifarnib administered at a starting dose of 300 mg, orally with food, bid on days 1 - 21 in 28 day cycles. Stepwise 100 mg dose reductions to control treatment-related, treatment-emergent toxicities are allowed and further detailed in [Section 9.5](#). Subjects who received tipifarnib bid on days 1 – 7 and days 15 – 21 in 28 day cycles during the conduct of earlier versions of this protocol may remain on that dose regimen at the discretion of the investigator. Alternatively, the subject may transition to receive a dose of 300 mg, orally with food, bid on days 1-21 of 28 day treatment cycles beginning on Day 1 of their next cycle.

Subjects may use proton pump inhibitors or H2 antagonists during the treatment portion of this study. However, subjects should be instructed to use antacids (magnesium or aluminum containing products) at least 2 hours before or after intake of oral study drug.

In the absence of emerging unmanageable toxicity, subjects may continue tipifarnib treatment for as long as the investigator considers that the treatment is providing clinical benefit up to 12 months since the subject's enrollment. Treatment may continue beyond 12 months upon agreement by the Investigator and Sponsor if there is documented evidence of sustained clinical benefit.

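### The 82.6% probability attached to the 12-subject AITL cohort does not follow from that cohort's data alone; give the cohort-only value and name the method

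*Protocol*

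**What the plan says.** Protocol Section 12.4 sets the cohort size: "An AITL cohort will be enrolled ($N = 12$) according to Amendment 4 to the protocol". It then says that "if 4 or more responses are observed, the probability that the true response rate in AITL subjects is at least 30% is 82.6" per cent, refers to Table 6, and ties the probability expressly to this sample size. The Synopsis (Statistical Methods) and Section 8.1 repeat the statement. Both introduce it with the reason for opening the cohort: "2 subjects enrolled with AITL and both subjects achieved a partial response".

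The CXCL12+ cohort, also of 12, has a sentence of the same form. Section 12.4 says "if 2 or more responses are observed, the probability that the true response rate in CXCL12+ subjects is 10% or higher is at least 87" per cent. Section 8.1 says "the probability that the true response rate in CXCL12+ subjects is at least 10% is at least 89" per cent, and the Synopsis also gives 89%.

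The text supplied names no prior or formula for any of these figures. Tables 6 and 7 are not in it, so the method may be given there.

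**The concern.** Four of 12 is an observed rate of 33%, barely above the 30% target, in a very small sample. A probability of nearly 83% that the true rate is at least 30% looks too high for that result. If the true rate were exactly 30%, four or more responses in 12 would occur about half the time (50.7%).

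The 82.6% is the only probability the protocol attaches to the AITL threshold. A reader who takes it as a property of the 12-subject cohort may credit the threshold with more evidence than 4 of 12 supplies. If the two earlier responders are in the calculation, the observations that prompted the cohort also raise its stated probability, and the sentence does not say so.

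**Working it through.** **Inputs.** From the protocol: n = 12, threshold x = 4, target rate 0.30, stated value 82.6% (Section 12.4); 2 responses in 2 earlier AITL subjects (Section 8.1); CXCL12+ n = 12, x = 2, target 0.10, stated values 87% (Section 12.4) and 89% (Section 8.1, Synopsis). The priors are assumptions.

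**Formulas.**
- Posterior at the threshold, prior Beta(a, b): P(p ≥ t | x, n) = 1 − BetaCDF(t; a + x, b + n − x). With a uniform prior this equals P(Bin(n + 1, t) ≤ x).
- Binomial form: P(X ≤ x | n, t).
- Literal conditioning on X ≥ x: the average of the posteriors for x, x + 1, …, n, weighted by their prior predictive probabilities.

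**Step 1. Calibrate on the CXCL12+ figures (2 of 12, target 0.10).**
- Uniform prior: P(Bin(13, 0.10) ≤ 2) = 0.2542 + 0.3672 + 0.2448 = 0.866, against a stated 87%.
- Binomial form: P(Bin(12, 0.10) ≤ 2) = 0.2824 + 0.3766 + 0.2301 = 0.889, against a stated 89%.
- Literal conditioning on two or more (uniform prior): 98.4%, which matches neither.

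Both figures are thus recovered, to rounding, by evaluating at exactly the threshold count.

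**Step 2. Apply the same formulas to 4 of 12, target 0.30.**
- Uniform prior: P(Bin(13, 0.30) ≤ 4) = 0.0097 + 0.0540 + 0.1388 + 0.2181 + 0.2337 = 0.654.
- Binomial form: P(Bin(12, 0.30) ≤ 4) = 0.0138 + 0.0712 + 0.1678 + 0.2397 + 0.2311 = 0.724.

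**Step 3. Other methods.**

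| Method, cohort data only | Exactly 4 of 12 | Four or more of 12 |
|---|---|---|
| Uniform prior | 65.4% | 93.4% |
| Jeffreys prior | 61.4% | 94.4% |
| Haldane prior | 57.0% | not computed |
| Beta(0.3, 0.7) prior | 56.7% | 90.7% |
| Binomial P(X ≤ 4) | 72.4% | not applicable |
| Binomial P(X ≤ 3), stricter form | 49.3% | not applicable |

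None of these is near 82.6%. To reach it at exactly 4 of 12, a prior worth one subject is not enough whatever its mean (maximum 72.4%), and a prior worth two subjects would need a mean of about 97%. Exactly 5 of 12 with a uniform prior gives 1 − BetaCDF(0.30; 6, 8) = 83.5%.

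**Step 4. Possible origin.** Adding the earlier 2 of 2 gives 6 of 14. With a Beta(0.3, 0.7) prior (mean 30%, weight one subject) the posterior is Beta(6.3, 8.7), and P(p ≥ 0.30) = 82.62%. With other priors 6 of 14 gives 83.5% (Haldane), 85.3% (Jeffreys) and 86.9% (uniform). This match was found by searching over priors and counts. An informative prior can also come close without pooling: Beta(4, 4), from the 4 responses in 8 PTCL subjects in the earlier lymphoma study (Section 5.2), gives 81.8% with 4 of 12.

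**Step 5. The earlier AITL count.** Section 5.2 reports all AITL subjects as "n = 23, 17 evaluable". Of these, 16 were in the AITL cohort and 4 in the CXCL12+ cohort, leaving 23 − 16 − 4 = 3 early subjects against the two in Section 8.1. The responders agree, however: 9 in all (5 CR, 4 PR), less 5 in the AITL cohort (3 CR, 2 PR), less the 2 AITL responders in the CXCL12+ cohort (both CR), leaves exactly 2 early PRs.

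**The case against.** The strongest reply is that Table 6 was not available to this review and may state the prior and data used. If it shows 6 of 14 with a Beta(0.3, 0.7) prior, the arithmetic is right, and the point reduces to the text not saying that earlier subjects are included. The Synopsis and Section 8.1 do mention the two earlier responders just before the figure, and the sentence concerns the true rate in AITL subjects generally. This stands as a reason not to call the figure a proven miscalculation. It does not rescue the wording, which attributes the figure to a sample size of 12.

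A reader might infer that the figure is simply overstated by 10 to 26 points (82.6% less 72.4% or 56.7%). The documents do not support that without qualification. The sentence says four or more, and read literally the value is 91% to 94%, which would make 82.6% too low. The at-threshold reading is preferred because it reproduces the CXCL12+ figures, but the range covers assumed methods, and the stricter binomial form falls below it.

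A reader might also infer from Section 5.2 that the earlier 2 of 2 was wrong. It does not show this. The responder totals leave exactly two early partial responses, and later enrolment, classification or a wider meaning of early phases could explain a third subject.

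The practical impact is small. SAP Section 4 describes 95% confidence intervals by number of responders in a 12-subject cohort, the primary test in SAP Section 8.1 concerns overall ORR against 10%, and the 20-subject extension tests no hypothesis. Section 5.2 also reports that "16 patients were enrolled with 11 being evaluable for efficacy", with 5 responses; 5 of 11 gives about 88% with a uniform prior. That later result does not make a statement about 4 of 12 correct.

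**Conclusion.** The point holds in limited form. With vague priors or the binomial formula, 82.6% does not follow from 12 subjects at the stated threshold: at exactly 4 of 12 the value is about 65% (uniform prior), 57% to 61% (the other vague priors tried) or 72% (binomial form), and conditioning on four or more gives about 91% to 94%. Preferring the at-threshold values rests on the protocol having treated its two 12-subject cohorts alike. Pooling with the earlier two responders is a possible origin, not a documented one. The defect is a stated design property that does not match the sample size it is attached to. It affects how the AITL threshold is described, not any test or planned analysis. The difference between two and three early AITL subjects is a secondary matter to reconcile.

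**What to change.** In the Synopsis, Section 8.1 and Section 12.4, and in Table 6 if it carries the same value, do one of the following:

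- Replace 82.6% with the value for 4 of 12 from the cohort alone and name the method. For example: with 4 of 12 responses the posterior probability (uniform prior, cohort data only) that the true rate is at least 30% is 65%; with 5 of 12 it is 83%.
- If the earlier 2 of 2 are included, say so, state the prior, and give the cohort-only value beside the pooled one.

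State whether the probability is for exactly the threshold count or for that count or more. Add a sentence reconciling the two early AITL subjects in the Synopsis and Section 8.1 with the three implied by Section 5.2.

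The cost is wording only. The cohort-only figure at the threshold is less favourable; sample size, hypothesis tests and SAP analyses are unchanged.
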